6.3 Exclusion Criteria

Patients meeting any of the following criteria are not eligible for participation in the study:

- 1. Existence of any life-threatening co-morbidity or any other medical condition which, in the opinion of the investigator, makes the patient unsuitable for inclusion.
- 2. History of hypersensitivity to ciclesonide.
- 3. Treatment with inhaled or intranasal corticosteroids within 14 days of the screening/ enrollment/randomization visit.
- 4. Treatment with oral corticosteroids within 90 days of the screening/enrollment/ randomization visit.
- 5. Participation in any other clinical trial or use of any investigational agent within 30 days of the screening/enrollment/randomization visit.
- 6. Currently receiving treatment with hydroxychloroquine/chloroquine.
- 7. Patients with cystic fibrosis.

- 8. Patients with idiopathic pulmonary fibrosis.
- 9. Pregnancy (for females of childbearing potential).

6.4 Withdrawal Criteria

Patients have the right to withdraw from the study at any time for any reason. Patients may also be withdrawn by the investigator at any time during the study for any of the following reasons:

- Patient, parent/legal guardian, or legally-authorized representative requests withdrawal.
- Patient experiences an adverse event requiring withdrawal from the study.
- Patient is noncompliant with the study schedule.
- Investigator believes it is in the best interest of the patient's health.

The medical monitor must be notified immediately for any of these instances to discuss follow-up plans. The data monitoring committee (DMC) (see section 7.3) should also be notified of patient withdrawals for any reason. When a patient withdraws before completing the study, the reason for withdrawal is to be documented in the eSource. Early termination procedures should be completed (see section 5.3.4).

Patients who are withdrawn from the study will not be replaced.

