5.2 Study Schedule

The time and events schedule for this study is provided in Table 1.

| Table 1.Schedule of Events | | | | |
|--|--|--|---------------------------------------|----------------------|
| | Screening/Enrollment/Randomization Visit (Day 1) | Treatment Period (Day 1 through Day 30) | Follow-up Period (Through Day 60) | Early Termination |
| Informed consent | X (before administration of any study-specific procedures) | | | |
| Inclusion/exclusion criteria review | X (predose) | | | |
| Prior/concomitant medication review | X (predose) | X (collected during patient contacts) | | |
| Demographic data and medical history ^a | X (predose) | | | |
| Physical examination, vital signs, height, weight, and calculation of body mass index | X (predose) | | | |
| Urine pregnancy test (for females of childbearing potential only) | X (predose, within 48 hours prior to enrollment) | | | |
| Confirm positive COVID-19 diagnostic test ^b | X (predose) | | | |
| Randomization | X (predose) | | | |
| Dispensing of IP, eDiary, and pulse oximeter | X (predose) | | | |
| Training on MDI inhalation technique (including rinsing of mouth with water following inhalation of IP), use of eDiary, and use of pulse oximeter | X (predose) | | | |
| Assess severity of COVID-19-related symptoms of cough, dyspnea, chills, and feeling feverish using a 4-point scale | X (predose) | X (BID [AM and PM] \leq 1 hour prior to IP administration, record in eDiary) ^c | | |
| Assess presence/absence of COVID-19- related symptoms of repeated shaking with chills, muscle pain, headache, sore throat, and new loss of taste or smell | X (predose) | X (BID [AM and PM] \leq 1 hour prior to IP administration, record in eDiary) ^c | | |
| Oxygen saturation levels | X (predose) | X (BID [AM and PM] \leq 1 hour prior to IP administration, record in eDiary) ^c | | |
| Collection of nasopharyngeal sample for viral load analysis | X (predose) | X (day 30 [window of $+ 2$ days]) ^d | | |
| IP administration | X | X (BID [AM and PM], record in eDiary) ^{c} | | |
| Adverse events | X (record any adverse events that occur following signing of informed consent) | X (collected during patient contacts) | X (collected during patient contacts) | X ^f |

| Table 1.Schedule of Events | | | | |
|---|---|--|--|----------------------|
| | Screening/Enrollment/Randomization Visit (Day 1) | Treatment Period (Day 1 through Day 30) | Follow-up Period (Through Day 60) | Early Termination |

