| HCP to contact patient for health status check, to collect adverse event and concomitant medication information, and to confirm/clarify information recorded in eDiary ^e | | X (days 2, 4, 6, 8, 10, 12, 14, 21 ± 2 days, and 30 ± 2 days) | | |
| Return of eDiary and investigational product (ie, used and unused MDIs) | | X (day 30 [window of $+ 2 \text{ days}])^d$ | | Х |
| HCP to contact patient to collect follow-up safety and outcome data | | | X (day 37 ± 4 days and day 60 ± 7 days) | \mathbf{X}^{f} |
| AM = morning (prior to noon); BID = twice a day; COVID-19 = coronavirus disease 2019; eDiary = electronic diary; HCP = healthcare provider; IP = investigational | | | | |

product; MDI = metered-dose inhaler; PM = evening (prior to midnight); SARS-CoV-2 = Severe Acute Respiratory Syndrome Coronavirus 2.

- a^{a} = To include date of onset of COVID-19 symptoms.
- = To meet criteria for inclusion, patient must have a positive SARS-CoV-2 molecular or antigen diagnostic test within 72 hours prior to enrollment.
- ^c = Note on day 1 dosing: In the event the patient receives the initial dose of IP at or before noon during the screening/enrollment/randomization visit, this will be considered to be the day 1 AM dose and the patient will be instructed to perform symptom assessments and oxygen saturation level monitoring, and to self-administer the day 1 PM dose prior to midnight. In the event the patient receives the initial dose of IP any time after noon during the screening/enrollment/randomization visit, this will be considered to be the day 1 PM dose and the patient will be instructed to wait until morning to perform symptom assessments, oxygen saturation level monitoring, and to self-administer the next dose (ie, day 2 AM dose). Note on day 30 dosing: Patients will be instructed to continue dosing through day 30. In the event the patient has their day 30 (window of + 2 days) visit on day 30, they will be instructed to perform symptom assessments and oxygen saturation level monitoring, and to self-administer the day 30 doses as per their typical schedule/routine. Thus, depending upon the time of day that the day 30 visit occurs, patients may or may not receive both doses on day 30. For patients that have their day 30 visit on day 31 or day 32, they will be instructed to complete through the day 30 PM dose and then discontinue investigational product dosing, symptom assessments, and oxygen saturation level monitoring.

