5.3.4 Early Termination Procedures

In the event of early termination, all ongoing non-serious adverse events will be followed until resolution, stabilization, or study day 60, whichever comes first; all ongoing serious adverse events will be followed until resolution or resolution with sequelae. Patients should be instructed to return the eDiary and investigational product (ie, used and unused MDIs) to the study site in a timely manner.

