11 QUALITY CONTROL AND QUALITY ASSURANCE

11.1 Conduct of the Study

Covis shall implement and maintain quality control and quality assurance procedures with written Standard Operating Procedures to ensure that the study is conducted and data are generated, documented, and reported in compliance with the protocol, ICH Good Clinical Practice (GCP), and applicable regulatory requirements.

This study is to be conducted according to globally accepted standards of GCP (as defined in the ICH E6 Guideline for GCP, 1 May 1996), in agreement with the latest revision of the Declaration of Helsinki and in keeping with local regulations.

The investigator should ensure that all persons assisting with the trial are adequately qualified, informed about the protocol, any amendments to the protocol, the study treatments, and their trial-related duties and functions.

The investigator should maintain a list of sub-investigators and other appropriately qualified persons to whom he or she has delegated significant trial-related duties.

The investigator may not deviate from the protocol without a formal protocol amendment having been established and approved by an appropriate Independent Ethics Committee (IEC)/IRB, except when necessary to eliminate immediate hazards to the patient or when the change(s) involve(s) only logistical or administrative aspects of the study. Any deviations may result in the patient having to be withdrawn from the study and render that patient nonevaluable.

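### Withdrawal for schedule noncompliance can end symptom-diary collection, so outcomes that the primary and day-14 estimands target may never be collected

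*Combined protocol and SAP*

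**What the plan says.** Section 6.4 lists grounds on which the investigator may withdraw a patient from the study. One is "Patient is noncompliant with the study schedule". For every ground the section adds "The medical monitor must be notified immediately for any of these instances to discuss follow-up plans", and it sends withdrawn patients to the early termination procedures of section 5.3.4. It also states "Patients who are withdrawn from the study will not be replaced".

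Section 5.3.4 contains two things: follow-up of ongoing adverse events, and the sentence "Patients should be instructed to return the eDiary and investigational product". In Table 1 (section 5.2), the row "Assess severity of COVID-19-related symptoms of cough, dyspnea, chills, and feeling feverish using a 4-point scale", the matching presence/absence row and the row for calls on days 2 to 30 are blank under Early Termination. The row "HCP to contact patient to collect follow-up safety and outcome data" is marked there, with a footnote that describes adverse-event follow-up.

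Sections 4.3.1 and 4.3.2 define the primary estimand (time to alleviation by day 30) and the key secondary one (alleviation by day 14). Both use a treatment-policy strategy for rescue medication, protocol violations and stopping product, and both say that data observed on study will be analysed. Section 10.2 puts every randomised patient in the ITT population. Section 10.7.1 leaves missing-data handling to the SAP and plans a tipping-point analysis. Section 11.1 ends a paragraph on the investigator departing from the protocol with "Any deviations may result in the patient having to be withdrawn from the study and render that patient nonevaluable".

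**The concern.** A treatment-policy estimand needs outcomes observed after the events that it disregards. Here one such event, on the ordinary reading that schedule noncompliance is a protocol violation, is also a ground for withdrawal, and the written withdrawal procedure takes away the instrument that records the outcome. Alleviation needs at least three successive symptom-free AM/PM assessments, and section 7.1.2 has these recorded in the eDiary.

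Hospitalised and deceased patients have a stated value under the composite rule. A non-hospitalised patient withdrawn before alleviation has neither a stated value in the protocol nor continued collection. For such patients the treatment comparison would rest on a missing-data assumption instead of data. What is at stake is bias and dependence on that assumption.

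**Working it through.** **1. The sections side by side**

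| Question | Where | Answer |
|---|---|---|
| Does a protocol violation change the target? | 4.3.1, 4.3.2 | No |
| Can schedule noncompliance end participation? | 6.4 | Yes, at the investigator's discretion |
| What follows? | 6.4, 5.3.4 | Early termination; eDiary returned |
| Are symptom entries or day 2 to 30 calls marked then? | Table 1 | No |
| Does any section require diary data to day 30 after withdrawal? | 6.4 | No; follow-up plans are discussed, content open |

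Each link is in the text, so the loss can occur when the rules are followed as written.

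**2. The plan's own figures (section 10.1)**

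Inputs: medians 7 and 11 days, HR about 1.58, 90% power, alpha 0.05 (taken as two-sided), 30 days, 1:1 allocation.

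- Schoenfeld events: 4 × (1.960 + 1.282)² / (ln 1.58)² = 200.9, so 201. This reproduces.
- Exponential 30-day event probabilities: 1 − 2^(−30/7) = 0.949 and 1 − 2^(−30/11) = 0.849; mean 0.899.
- Base N: Freedman's formula with HR 1.58 gives 208 events, and 208/0.899 rounds up to 232. This matches. (201/0.899 gives 224.)
- Events expected with 400 patients: 400 × 0.8989 = 359.5.

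**3. Power**

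Power = Φ(√D/2 × ln(11/7) − 1.96). For D = 359.5 this is Φ(2.33) = 99.0%; for D = 330, Φ(2.15) = 98.4%. With 10% leaving on days 2 to 10 and censored, expected events are 332 to 338, against the 201 required.

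**4. How many outcomes could be lost**

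The protocol calls drop-out unknown and gives no share for this route, so every rate here is an assumption. If leaving is uniform on days a to b and uninformative, the chance of leaving before alleviation is (m/ln 2) × (2^(−a/m) − 2^(−b/m)) / (b − a), with m the median. At 10%, 20 of 200 patients per arm leave:

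- Days 2 to 10: ciclesonide 20 × 0.567 = 11.3; placebo 20 × 0.692 = 13.8.
- Days 2 to 30: ciclesonide 20 × 0.277 = 5.5; placebo 20 × 0.414 = 8.3.

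Allowing for leavers who recover at half rate, the ranges are 11 to 15 and 14 to 17 (days 2 to 10), or about 5 to 10 and 8 to 12 (days 2 to 30). At 2% on days 2 to 10 they are 2 to 3 and about 3.

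**5. Effect on the hazard ratio**

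Large-sample Cox simulation: exponential recovery, 1,000,000 patients per arm, follow-up to day 30.

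| Leaving per arm | Days | Leavers at half rate in | HR, full follow-up | HR, censored at leaving | Shift |
|---|---|---|---|---|---|
| 10% | 2–10 | neither arm | 1.569 | 1.570 | 0.00 |
| 10% | 2–10 | both arms | 1.547 | 1.566 | +0.02 |
| 10% | 2–10 | ciclesonide only | 1.446 | 1.531 | +0.09 |
| 10% | 2–10 | placebo only | 1.682 | 1.608 | −0.07 |
| 10% | 2–30 | ciclesonide only | 1.449 | 1.491 | +0.04 |
| 10% | 2–30 | placebo only | 1.681 | 1.646 | −0.04 |
| 5% | 2–10 | ciclesonide only | 1.507 | 1.555 | +0.05 |
| 5% | 2–10 | placebo only | 1.630 | 1.593 | −0.04 |
| 2% | 2–10 | ciclesonide only | 1.546 | 1.565 | +0.02 |
| 2% | 2–10 | placebo only | 1.597 | 1.583 | −0.01 |

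At 2% on days 2 to 30 the one-arm shifts are about 0.01.

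The handling rule matters even when leaving is uninformative. At 10%, counting leavers as failures to day 30 gives HR 1.50 (days 2 to 10) or 1.54 (days 2 to 30), against 1.57 when they are censored.

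**6. Day-14 difference**

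At 10% on days 2 to 10, the largest movement is in the placebo-only case: 18.6 points with full follow-up against 16.7 among completers, a change of 1.9 points.

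**The case against.** The strongest reply is that nothing in the plan is broken. Withdrawal from the study is not among the listed intercurrent events, both estimand sections speak of data observed on study, and absent data are assigned to the SAP and a tipping-point analysis. This stands in part: it is a gap in retention wording, and sections 10.2 and 10.7.1 promise only that all randomised patients are analysed. But those provisions govern how gaps are analysed. They do not collect the outcomes, and the estimand still targets them.

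Second, follow-up is not excluded. The medical monitor must be contacted, and Table 1 marks an early-termination contact whose row label mentions outcome data. That is fair. Yet the content of the follow-up plan is left open. The footnote on that contact describes adverse events, although it does not say it is limited to them. The row's scheduled contacts, around days 37 and 60, cannot rebuild twice-daily entries.

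Third, the larger shifts need leavers who recover more slowly in one arm only, in a blinded trial, and they depend on when leaving happens. This stands and limits the size claimed.

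Fourth, patients withdrawn for noncompliance may be the ones who do not fill in diaries. This also stands, so recovery would be partial.

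**Conclusion.** The point holds as a mismatch between withdrawal procedure and estimand. For non-hospitalised patients withdrawn at the investigator's discretion before alleviation, the primary and day-14 outcomes can be lost. Patients who reached alleviation before leaving lose nothing on these endpoints. The size is unknown and probably modest, and rests on the assumed leaving rates, timing and recovery in the working.

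Four stronger readings may tempt a reader, and the documents do not support them:

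- *Stopping product ends the diary.* No section says so. Section 9.2.3 lists product withdrawal as an action in its own right, and section 5.1 names product and scheduled procedures separately.
- *Patients with deviations are dropped from the analysis, or any patient deviation is a route out.* The section 11.1 sentence is discretionary and belongs to a paragraph on investigator deviations. Its term nonevaluable is undefined and conflicts in wording with ITT; sections 10.2 and 10.7.1 govern the analysis.
- *Power is harmed.* It stays near 98% or above at 10% leaving.
- *The false-positive rate is inflated.* That needs unequal withdrawal plus a failure rule. With no true effect, 5% v 10% withdrawn and counted as failures at day 14 would give a false difference of 2.9 points and about 9% rejection; equal withdrawal leaves it at 5%. The documents give no ground for expecting unequal withdrawal, and the protocol sets no such rule for these patients.

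**What to change.** 1. In sections 6.4 and 5.3.4 and in Table 1, state that schedule noncompliance or a deviation does not by itself end data collection. Non-hospitalised patients who are willing, and whose consent to data collection stands, keep the eDiary and continue AM/PM symptom entries and the scheduled calls through day 30. Separate return of the eDiary from return of product, and mark the affected Table 1 rows to match.
2. In section 11.1, delete the clause that makes the patient nonevaluable, and state that such patients remain in the ITT population.
3. Record the date and reason for end of product use and for end of data collection as separate items.

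This concerns data collection only. Decisions on continuing or stopping product, and withdrawals for adverse events or in the patient's best interest, are left as they are.

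The cost is amendment wording, site retraining and some extra diary and call follow-up. Section 5.3.2 ties entries to dosing, so entry times would have to be written for any of these patients no longer taking product. If half of the leavers were kept (an assumption), the one-arm shifts at 10% on days 2 to 10 would fall from 0.07–0.09 to about 0.04. Patients who withdraw consent, or who do not complete diaries, would still be missing.

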7 STUDY ASSESSMENTS AND PROCEDURES

7.1 Efficacy

7.1.1 Efficacy Endpoints

The primary efficacy endpoint is:

• Time to alleviation of COVID-19-related symptoms of cough, dyspnea, chills, feeling feverish, repeated shaking with chills, muscle pain, headache, sore throat, and new loss of taste or smell, defined as symptom-free for a continuous period of ≥ 24 hours (ie, ≥ 3 AM/PM assessments) by day 30

The secondary efficacy endpoints for the study are:

- Percentage of patients with hospital admission or death by day 30
- All-cause mortality by day 30
- COVID-19-related mortality by day 30
- Percentage of patients with subsequent emergency department visit or hospital admission for reasons attributable to COVID-19 by day 30
- Percentage of patients with alleviation of COVID-19-related symptoms of cough, dyspnea, chills, feeling feverish, repeated shaking with chills, muscle pain, headache, sore throat, and new loss of taste or smell, defined as symptom-free for a continuous period of ≥ 24 hours (ie, ≥ 3 AM/PM assessments) by day 7, by day 14, and by day 30
- Time to hospital admission or death
- Change from baseline in oxygen saturation levels
- Change from baseline in COVID-19 viral load in nasopharyngeal sample at day 30

7.1.2 Efficacy Assessments

7.1.2.1 Assessment of COVID-19-Related Symptoms of Cough, Dyspnea, Chills, and Feeling Feverish

Patients will assess severity of COVID-19-related symptoms of cough, dyspnea, chills, and feeling feverish using a 4-point scale where 0 = absent, 1 = mild, 2 = moderate, and 3 = severe. Assessment of these symptoms will be performed predose during the screening/enrollment/ randomization visit. During the 30-day treatment period, patients will be instructed to assess these 4 symptoms using a 4-point scale at a frequency of BID prior to self-administration of the investigational product (ie, within 1 hour of administration). The patient will record results in the eDiary.

7.1.2.2 Presence/Absence of COVID-19-Related Symptoms of Repeated Shaking with Chills, Muscle Pain, Headache, Sore Throat, and New Loss of Taste or Smell

Patients will assess the presence/absence of COVID-19-related symptoms of repeated shaking with chills, muscle pain, headache, sore throat, and new loss of taste or smell. Assessment of these symptoms will be performed predose during the screening/enrollment/randomization visit. During the 30-day treatment period, patients will be instructed to assess presence/absence of these symptoms at a frequency of BID prior to self-administration of the investigational product (ie, within 1 hour of administration). The patient will record results in the eDiary.

7.1.2.3 Oxygen Saturation Levels

Oxygen saturation levels will be measured predose during the screening/enrollment/ randomization visit. During the 30-day treatment period, patients will be instructed to measure oxygen saturation levels (using the provided pulse oximeter) at a frequency of BID. The patient will record results of all assessments in the eDiary. The patient will be instructed to seek medical attention immediately should oxygen saturation levels fall to 93% or below.

7.1.2.4 Viral Load Analysis

A nasopharyngeal swab for viral load analysis will be collected by study personnel predose during the screening/enrollment/randomization visit and on day 30 (window of + 2 days). For each patient, the same nostril should be used for collection of samples at both time points, if possible. Sample collection, handling, labeling, storage, shipping, and methods of analysis will be performed according to procedures specified in separate documents.

7.2 Safety

7.2.1 Safety Endpoint

Safety will be assessed based on adverse events.

7.2.2 Safety Assessments

Adverse events will be recorded starting with the signing of the ICF. Adverse events occurring during the screening/enrollment/randomization visit will be recorded by study personnel in the eSource. Information regarding adverse events occurring during the 30-day treatment period and post-treatment adverse events occurring during the follow-up period will be collected by qualified healthcare providers during the scheduled patient contacts and recorded in the eSource.

Any new infection that occurs on study, regardless of the infecting agent (ie, viral or non-viral) should be captured as an adverse event. In these cases, the site of infection and source of culture (eg, bronchoalveolar lavage, tracheal aspirate, sputum, blood, urine) should be recorded.

Section 9 contains additional information regarding to adverse events.

7.3 Data Monitoring Committee

An independent and appropriately constituted DMC will be organized for this study. A charter detailing the purpose of the committee as well as their roles and responsibilities will be put into place and will guide and direct their actions.

